#### 9.8 Rescue Medication

Sites should have immediate access to rescue medications for the following reactions in this trial:

REDACTED Version 8.0, 18/JUN/2024; IRAS ID: 1008179 MORE-KARE protocol

Page 71 of 105

- 1. Allergic reaction if a participant has an allergic reaction to the IMP they should be withdrawn from the trial. Rescue medication and resuscitative equipment should be immediately available for such an event.
- 2. Intolerable emergence phenomenon varying reactions to the IMP are expected in this trial, however if emergency phenomena are intolerable to a participant during an infusion the infusion should be stopped in the first instance, these effects should remit very rapidly. Alternatively the co-administration of a benzodiazepine; lorazepam can be administered by the trial medic
- 3. Nausea participants will fast for 6 hours before an infusion to reduce the risk of vomiting and pulmonary aspiration. In the case of vomiting, or if nausea is intolerable to the participant, then the trial medics can offer medication (e.g. ondansetron) to ease nausea or the infusion should be stopped, whereupon these symptoms should remit very quickly.

#### 9.9 Known drug reactions and interaction with other therapies

See SmPC and risk section 3. Note that the SmPC relates to anaesthetic dose levels of ketamine, this trial uses lower doses.

#### 9.10 Concomitant medication

Ketamine interacts with the following substances and therefore their concomitant use will not be permitted during active treatment days: barbiturates and/or narcotics, atracurium and tubocurarine, central nervous system (CNS) depressants (e.g. phenothiazines, sedating H1 – blockers or skeletal muscle relaxants), thiopental, thyroid hormones, theophylline and other methylxanthines, sympathomimetics and vasopressin, ergometrine, and drugs that inhibit/induce CYP34A enzyme activity e.g. anti-psychotics.

Due to potential impacts on the primary outcomes taking any other alcohol relapse prevention medication will not be permitted during the period of trial (Visit 2 - Visit 8).

The delegated trial site team will ask participants about concomitant medication prior to confirmation of eligibility and a list of restricted concomitant medications will be sent to the participant's GP at the time of confirming eligibility. Participants that are unable to stop taking restricted medication will be unable to enter the trial. For specifics regarding cannabis use please see section 8.9.2. Participant-reported
concomitant medication reviews will also take place at all trial visits to continue to review eligibility and document concomitant medication use. All concomitant medication use should be recorded in the concomitant medication eCRF and reviewed by a delegated RN or trial medic.

# 9.11 Trial restrictions

Ketamine is an analgesic agent and participants will be required to fast (nil by mouth excluding water) for six hours prior to infusion and completely (i.e. no water) 2 hours prior. Confirmation from the participant about last consumed food/drink will be required on infusion days and if the window is not met infusions will be delayed.

# 9.12 Assessment of compliance with treatment

Compliance includes adherence to both to IMP and protocol trial procedures. The trial medication will be administered by the research medic/nurse only in the context of the participant attending the trial site facility. Participants will not be responsible for any trial medication. A member of the site team will ensure that the arrangements for each treatment visit are agreed with the participant. Where necessary, the site team will assist in transportation. If a participant fails to attend a clinic visit for the infusion then the site team will endeavour to contact the participant to identify the reason. Where possible an alternative appointment will be made within the infusion visit window (see Table 2 page 46). If the participant fails to attend a clinic visit for the follow-up day the site team will endeavour to contact the participant to identify the reason and where possible arrange an alternative visit within the follow-up visit window (see Table 2 page 46). All episodes of failure to attend visits will be recorded in the medical notes, eCRF and protocol deviation log (eCRF). If the participant misses 2 consecutive infusions, then they will be withdrawn from treatment and will be invited to attend follow up visits 9 and 10 as part of our intention to treat protocol. Non-compliance to the protocol trial procedures will be documented by the site team and reported to ExeCTU via the eCRF. Persistent non-compliance (attendance <80% for treatment visits i.e. visits 2-8) may lead the participant to be withdrawn from the trial.

# 10 PHARMACOVIGILANCE

# 10.1 Definitions

Adverse event (AE)

Any untoward medical occurrence in a participant to whom a medicinal product has been administered, including occurrences which are not necessarily caused by or related to that product.

# Serious Adverse Event (SAE)

A serious adverse event is any untoward medical occurrence that occurs from time of consent up to 30 days post last IMP administration. After this period, investigators are still required to report any SARs that they become aware of until a participant's last visit:

- results in death
- is life-threatening
- requires in-patient hospitalisation or prolongation of existing hospitalisation
- results in persistent or significant disability/incapacity
- consists of a congenital anomaly or birth defect

Other 'important medical events' may also be considered serious if they jeopardise the participant or require an intervention to prevent one of the above consequences.

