# Related unexpected serious adverse event (RUSAE)

A RUSAE is an SAE that is related to the therapy/education and not listed in the protocol as an expected outcome.

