# 10.3 Reporting serious adverse events

Any event that meets the protocol definition of an SAE must be reported to ExeCTU and the Sponsor **within 24 hours** of the PI, designee or research team becoming aware of the event by completing an SAE eCRF in REDCap. In the even of a death a death eCRF should also be completed in REDCap.

ExeCTU and the Sponsor will be notified by email whenever a new SAE eCRF entry has been completed.

For each SAE the following information will be collected:

- Full details in medical terms with a diagnosis, if possible;
- Event duration (date of onset and date of resolution);
- Seriousness criteria;
- Causality, in the opinion of the PI (or designee);
- Action taken;
- Outcome;

In addition to the above, the following details will be collected for each SUSAR/RUSAE:

- Relevant medical history;
- Concomitant medications;
- Treatment for SUSAR/RUSAE;
- Relevant diagnostic tests.

All SAEs must be reviewed and signed by a Principal Investigator (PI) or designated representative.

It is the PI or designated representative responsibility that all SAEs/SARs/SUSARs/RUSAEs are followed up until the final outcome is reached or up to the end of the trial. All follow-up information should be entered into the eCRF as soon as the PI or designated representative becomes aware of the outcome. Ongoing SAEs/SARs/SUSARs/RUSAEs at the end of the trial will be followed up by the participant's GP and/or the routine clinical care team until discharge.

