# 10.4.3 DMC

In accordance with the DMC charter, the DMC will periodically review unblinded safety data for each treatment group separately to determine patterns and trends of events, or to identify safety issues that would not be apparent on an individual case basis.

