# 11.3.3 Handling of intercurrent events of primary estimands

Intercurrent events related to adherence to treatment (i.e. discontinuation/withdrawal) will be handled using the treatment policy strategy; the treatment effect is sought irrespective of the occurrence of an intercurrent event. This policy is in alignment with an ITT analysis. Deaths during the trial will be handled using the 'while alive' approach; participant data collected prior to death will be included in the analyses.

A principal stratum approach will be used to target the treatment effect in adherent participants (assuming that adherence status would be identical for a participant irrespective of the treatment group to which they were allocated). A per protocol analysis will compare adherent participants

REDACTED Version 8.0, 18/JUN/2024; IRAS ID: 1008179 MORE-KARE protocol Page 82 of 105

Participants will be considered as adherent if they received all three infusions at their allocated dose plus all their scheduled sessions as allocated. The per protocol approach is in alignment with a principal stratum approach. The resulting estimand therefore applies to the population of people who would be adherent to treatment as offered.

A per protocol analysis will be performed for the primary outcome and all secondary outcomes at 6month follow-up. There are limited opportunities within the trial for treatment switching

is no possibility for the participants to receive ketamine outside the trial, and participants are requested to refrain from beginning new psychological therapy during the active treatment phase. A participant could only receive the incorrect dose of ketamine if an error occurred in making up or administering the IMP.

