#### 11.3.4 Handling of missing data

As a sensitivity analysis for comparison with the treatment policy analysis (i.e. disregarding the intercurrent event of non-adherence to treatment) using observed data only, we will use multiple imputation to impute missing outcome data for the primary outcome and all continuous outcomes at 6 months (i.e. to address the intercurrent event of loss to follow-up). Multiple imputation using chained equations (MICE) will be used; the imputation algorithm will include baseline characteristics that are found to be predictive of missingness of the primary outcome, as well as treatment arm, baseline characteristics included in the primary and secondary analyses, baseline outcome scores, and minimisation variables. Logistic regression will be used to determine characteristics associated with missing primary outcome data (days of heavy drinking at 6-month follow-up). Predictive mean matching will be the method for imputing individual scores; the number of imputed datasets will be determined by the percentage of participants that have missing primary outcome data. Observed and imputed data will be used to perform a sensitivity analysis

at 6 months using the treatment policy approach. Imputation of missing data is based on the assumption that such data are missing at random (propensity for missingness is not related to the (unobserved) value of the missing data). The estimand derived from analyses of observed and imputed data therefore relates to the same population as that of the estimand derived from the primary analysis using observed data only. In the event of a participant death during the trial, data that would have been collected will be considered as non-existent rather than missing and will not be imputed.

REDACTED Version 8.0, 18/JUN/2024; IRAS ID: 1008179 MORE-KARE protocol Page 83 of 105

. There

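### After day 38 to 72 the protocol prescribes no collection of deaths judged unrelated to ketamine and no route for delayed therapy-related serious events, although its death-handling rules need deaths known to day 180

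*Protocol*

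**What the plan says.** Section 10.1 of the protocol puts a time limit on serious adverse events: "A serious adverse event is any untoward medical occurrence that occurs from time of consent up to 30 days post last IMP administration". It then makes one exception: "After this period, investigators are still required to report any SARs that they become aware of until a participant's last visit". The same section ties a SAR to suspected causality by the IMP, so the exception covers ketamine only. Section 10.2 applies the same 30-day limit to recording clinically significant adverse events, and Table 2 schedules adverse-event review at visits 2 to 8 but not at visits 9 or 10.

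Serious events linked to the other half of the intervention have their own category: "A RUSAE is an SAE that is related to the therapy/education" (with the further condition that it is not listed as expected). Sections 10.3.1 and 10.3.3 treat every such event as unexpected and send it to the ethics committee within 15 days. RUSAEs are not named in the late exception.

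On death, section 10.3 (serious-event reporting) says that "a death eCRF should also be completed in REDCap". Section 11.3.3 applies a 'while alive' approach to deaths during the trial: "participant data collected prior to death will be included in the analyses". Section 11.3.4 adds that after a death "data that would have been collected will be considered as non-existent rather than missing and will not be imputed", whereas other missing 6-month outcomes are imputed in a sensitivity analysis. Section 10.4.3 asks the DMC to review the groups separately and "identify safety issues that would not be apparent on an individual case basis".

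**The concern.** The safety sections and the analysis sections work to different clocks. The analysis rules distinguish a participant who died from one who was lost, at any time up to six months. The reporting rules prescribe full capture of deaths only until 30 days after the last infusion. After that, whether a death has to be reported depends on an investigator suspecting ketamine.

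A suicide or an alcohol-related death on day 100, judged unrelated to ketamine, has no stated reporting route. Section 8.12 classes a participant who cannot be contacted as lost to follow-up, and reports the PPI team's suggestion of one call and an email or letter. A death could therefore pass as ordinary loss. A serious event attributed to the therapy or education that appears after the window has no stated route either. What is at stake is correct use of the plan's own death rules, and an arm-by-arm account of deaths over the period in which efficacy is judged.

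**Working it through.** **Inputs.** Visit 2 (first infusion, randomisation) is day 0. Table 2 and section 8.7 place visit 4 at 4 to 21 days after visit 2, and visit 6 (third infusion) at 4 to 21 days after visit 4. Table 2 places visit 8 (last therapy or education session) at 4 to 14 days after visit 6, visit 9 at day 90 to 97 and visit 10 at day 180 to 187. The reporting window is 30 days after the last infusion (10.1).

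**Uncovered time.** Window close = day of last infusion + 30. Uncovered days = 180 − window close.

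| Schedule | Last infusion | Window closes | Uncovered days | Share of 180 |
|---|---|---|---|---|
| Shortest windows (4 + 4) | day 8 | day 38 | 142 | 79% |
| Weekly (7 + 7), section 9.6 | day 14 | day 44 | 136 | 76% |
| Longest windows (21 + 21) | day 42 | day 72 | 108 | 60% |
| First infusion only | day 0 | day 30 | 150 | 83% |

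Visits 9 and 10 fall outside the window in every row. The trial summary gives a treatment duration of 4 to 12 weeks. If the last infusion fell on day 70, the uncovered time would be 180 − 100 = 80 days (44%), but the visit windows do not allow that: visit 8 falls no later than day 42 + 14 = day 56.

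**Therapy and education.** For a participant who has all three infusions, the last session is 4 to 14 days after the third, so it lies inside the window. Cover after it is 30 − 14 = 16 days to 30 − 4 = 26 days. The gap concerns delayed events only.

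**Likely number of deaths.** The protocol gives no mortality rate. Assuming 0.25% to 2% over six months, deaths spread evenly over time, and 280 participants:

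- Expected deaths: 280 × 0.0025 = 0.7 to 280 × 0.02 = 5.6.
- After the window: 0.7 × 108/180 = 0.4 to 5.6 × 142/180 = 4.4.

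**Effect on the analyses.** Section 11.3.1 bases the primary analysis on observed data only, and multiple imputation is a sensitivity analysis (11.3.4). An unrecognised death would therefore be imputed in the sensitivity analysis, against the stated rule. In the primary analysis the issue is what happens to the pre-death record. Section 4.3.1 asks for at least 180 days of TLFB data, while 'while alive' keeps the shorter record of someone who died. The same partial record could be kept or dropped according to whether the death is known.

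**The case against.** Several points on the other side stand.

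- A reader might infer that late deaths are not collected at all. The text does not go that far. The death-form sentence has no time limit of its own; the limit comes only from its place within serious-event reporting. Section 9.12 has the site try to learn why a visit was missed, section 8.12 records reasons for withdrawal, and serious events already reported are followed to outcome or the end of the trial. What is missing is prescribed collection.
- A reader might infer that a late therapy-related event cannot be a RUSAE by definition. That is too literal. A SAR is also defined as an SAE, yet 10.1 expects late SARs, so the 30 days works as a reporting window. The narrower point remains: the exception names SARs and omits RUSAEs.
- A reader might infer that imputed post-death values enter the primary result. They do not, because imputation is confined to the sensitivity analysis.
- A reader might conclude that all serious events must be collected to visit 10. Comparing them by arm over six months is not a stated objective. The protocol describes three isolated low doses and a short half-life, which bear on a limited window, and it keeps SAR reporting to the last visit. The DMC charter is not shown, so its inputs cannot be assumed to stop at serious-event forms. Wider collection is largely a design preference.

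None of this supplies a rule under which every death to day 180 is recorded with its date.

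**Conclusion.** The point holds as a mismatch between the safety-reporting rules and the death-handling rules. For 60% to 79% of the 180 days (83% after a single infusion) there is no prescribed collection of deaths judged unrelated to ketamine. Delayed RUSAEs have no reporting route over the same period, although all sessions fall inside the window with 16 to 26 days of cover after the last one. The shares follow from the protocol's visit windows and need no outside assumption.

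The effect on the primary estimate is probably small. On the assumed mortality range it concerns about 0.4 to 4.4 deaths among 280 participants, and some of those would surface informally. The case for acting rests on consistency and on a complete count of deaths by arm, not on the size of any bias. This is a cheap improvement worth making, not an obstacle to the trial.

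**What to change.** In sections 10.1 and 10.3 and Table 2:

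1. Require the death eCRF, with date of death, for every death from randomisation to visit 10, whatever the cause.
2. Check vital status at the visit 9 and visit 10 time points, including for participants who do not attend.
3. Extend the late-reporting exception from SARs to SARs and RUSAEs.
4. Tabulate deaths by arm for the DMC and the final report.

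The 30-day window for unrelated serious events can otherwise stay; collecting all of them to visit 10 is optional. The cost is a protocol amendment and slightly more data entry, using a form that already exists and visits already scheduled.

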# In addition;

- Dissociative and psychotomimetic effects, analgesia, dizziness, lack of co-ordination, unsteadiness, impaired memory and impaired concentration are expected following infusion. Persistence of any of these effects two hours after the infusion should be reported as an SAE.
- Increased blood pressure. Persistent increased blood pressure e.g. ≥ 220 systolic for 30 minutes should be reported as an SAE

NOTE: The term "life-threatening" in the definition of "serious" refers to an event in which the participant was at risk of death at the time of the event; it does not refer to an event which hypothetically might have caused death if it were more severe.

# Serious adverse reactions (SAR)

A serious adverse reaction is an SAE that is suspected as having a causality to IMP, as assessed by the investigator or delegate responsible for the care of the participant.

# Suspected unexpected serious adverse reaction (SUSAR)

A SUSAR is a SAR that is not listed as expected for the IMP in the reference safety information (RSI) as assessed by the CI or nominated representative. The RSI for this trial is the summary of product characteristics (SmPC) section 4.8.

# Related unexpected serious adverse event (RUSAE)

A RUSAE is an SAE that is related to the therapy/education and not listed in the protocol as an expected outcome.

# 10.2 Reporting adverse events

For the purposes of this trial any clinically significant AE will be recorded from the time of consent up to 30 days post last IMP administration.

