# Table 2. Assessments to be carried out at each visit/time point.

	Pre- Screening (telephone)	Screenin g	Refresher Screening	Baseline		Treatment Phase					Follow Up		
Visit #	-1	1	1	2	3	4	5	6	7	8	9 F-UP	10 F-UP	Opportunistic 11 F-UP
		14 to 28 days before visit 2	Only to be run if 28 days elapses between screening and visit 2	14 to 28 days after screening	1 to 5 days after visit 2	4 to 21 days after visit 2	1 to 5 days after visit 4	4 to 21 days after visit 4	1 to 5 days after visit 6	4 to 14 days after visit 6	90-97 days after visit 2	180-187 days after visit 2	360-367 days after visit 2
Trial discussion with Participant	x	x	Х										
Pre Screening Questionnaire	x												
Informed Consent		X											
Medical History		X	х										
Physical a		Х	х										
SCID		X	Х								Х	Х	
Withdrawal symptom checklist				X h									

REDACTED Version 8.0 18/JUN/2024; IRAS ID: 1008179

Page 46 of 105

	Pre- Screening (telephone)	Screenin g	Refresher Screening	Baseline	Treatment Phase							Follow Up	
Visit #	-1	1	1	2	3	4	5	6	7	8	9 F-UP	10 F-UP	Opportunistic 11 F-UP
Vital Signs		Xp	Xp	X b, h, m	Xp	X b, m	Xp	X b,m	Xp	Xp			
Bloods		Хc	Xc	X d, j		X d		X d		X d	X d	X d	
Eligibility determination	Х	Х	Х	X h									
Urine Drug screen		Xe	Х	X e, h	Xť	Xe	Xf	Xe	Xf	Xe	Xe	Xe	
Pregnancy Test I POCBP		х	Х	X h		x		Х					
Breathalyser		Х	х	X h	x	X	Х	Х	Х	Х	Х	Х	
Randomisation				x									
Install / Check BACtrack App		Xa	Xa	X g, h		х		х		Х	Х	х	
Self-breathalyser				X h	Х	Х	Х	Х	Х	Х	Х	Х	
IMP administration				х		Х		Х					
Therapy/education				Х	Х	Х	Х	Х	Х	Х			
Adverse Events review				Х	Х	Х	Х	Х	Х	Х			
Concomitant Medication review		X	х	X h	х	х	Х	х	х	х	Х	х	
Alcohol and Drug Use History		Х	Х							Х	х	х	

REDACTED Version 8.0, 18/JUN/2024; IRAS ID: 1008179

Page 47 of 105

	Pre- Screening (telephone)	Screenin g	Refresher Screening	Baseline			Treatm	ent Phase				Follow Up	
Visit #	-1	1	1	2	3	4	5	6	7	8	9 F-UP	10 F-UP	Opportunistic 11 F-UP
Family history		х											
Demographic details	X k	XI											
BDI		Х	х	X i						Х	х	Х	Х
MADRS		Х	х	Xi						Х	х	Х	
Columbia Suicide Severity Rating Scale		х	х										
Alcohol Abstinence Self Efficacy Scale		Х		Xi						х	Х	х	
SHAPS		х		Xi		х		Х		Х	Х	Х	
ACQ-NOW		X		Xi	Х	Х	Х	Х	Х	Х	Х	Х	
KSET		Х	x	Xj		Х		Х		Х	Х	Х	
CADSS		х	Х	Xi		Х		Х		Х	Х	Х	

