#### 9.6 Dosage schedules

Three infusions will be administered at weekly intervals, one each at visits 2, 4 and 6. Doses will be made up from a neutral glass vial/ampoule with rubber closure and aluminium flip-off cap containing ketamine hydrochloride. The total amount to be delivered will be calculated on the basis of the participant's screening visit weight.

Site pharmacy / unblinded site staff will order ketamine and dispense per participant, added to saline (0.9%) to make up to 50ml solution in syringes/bags for the syringe/infusion pump to infuse intravenously over 40 minutes. Doses will be administered using a computer-controlled syringe pump if a syringe has been prepared, or a computer-controlled infusion pump if an infusion bag has been prepared.

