# 10.2.1 Expected AE's

The following AEs are expected disease related and/or procedural expected events:

- Bruising caused by venepuncture
- Dissociative and psychotomimetic effects, analgesia, dizziness, lack of co-ordination, unsteadiness, impaired memory and impaired concentration following infusion. Persistent effects two hours after the infusion should be reported as an SAE.
- Skin rash caused by the BACtrack Skyn device
- Increased blood pressure. Persistent increased blood pressure e.g. ≥ 220 systolic for 30 minutes should be reported as an SAE.
- Drinking lapse or relapse
- Emotional distress or anxiety caused by the psychological therapy or education sessions

Please note expected AEs should be documented in source data but are not required to be reported via the REDCap eCRF unless they meet the definition of an SAE. All unexpected AEs should be reported in both the source data and REDCap eCRF.

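### Adverse events are to be recorded for 30 days after the last dose, but the visit schedule stops asking about them at visit 8, which is 4 to 14 days after it

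*Protocol*

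**What the plan says.** Protocol section 10.2 fixes the recording window: "any clinically significant AE will be recorded from the time of consent up to 30 days post last IMP administration". The definition of a serious adverse event in section 10.1 uses the same window, and adds that serious adverse reactions which come to the investigator's notice later remain reportable until the participant's last visit.

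The dosing visits follow from section 9.6: "Three infusions will be administered at weekly intervals, one each at visits 2, 4 and 6". Table 2 places visit 8 "4 to 14 days after visit 6" and visit 9 "90-97 days after visit 2". Its row "Adverse Events review" is marked at visits 2, 3, 4, 5, 6, 7 and 8 and is blank at visits 9, 10 and 11.

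Section 8.12 invites participants who discontinue treatment to visits 9 and 10, and says that a participant who stops the infusions cannot continue the therapy or education sessions. Section 9.12 names the same two visits for someone withdrawn from treatment after missing two consecutive infusions.

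On expected events, section 10.2.1 says that "expected AEs should be documented in source data but are not required to be reported via the REDCap eCRF unless they meet the definition" of a serious adverse event. Unexpected events go into both source and eCRF. Section 10.4.3 says that "the DMC will periodically review unblinded safety data for each treatment group separately".

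**The concern.** A recording window is only as good as the enquiry that fills it. Section 10.2 sets the window at 30 days after the last dose, but the schedule that sites work from stops asking well before that. After visit 8, a non-serious event reaches the trial only if the participant volunteers it.

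The people most exposed are those who stop treatment early, some of them because of intolerance: section 9.7 withdraws from treatment anyone with intolerable side effects. Their remaining visits carry no adverse events review, so ascertainment is weakest where tolerability information may matter most.

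A second, smaller matter is what the adverse event form can show by arm. The expected list in section 10.2.1 includes dissociative and psychotomimetic effects, dizziness, unsteadiness, impaired memory and raised blood pressure. These are plausibly the effects most likely to differ between 0.8 and 0.05 mg/kg. If they are not serious, entry in the eCRF is not required, so form-based counts will be incomplete and may vary between sites.

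**Working it through.** The plan gives no calculated figure to reproduce, so the check is date arithmetic on the Table 2 windows, with visit 2 (first infusion) as day 0.

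**Inputs (Table 2):** visit 4 is 4 to 21 days after visit 2; visit 6 is 4 to 21 days after visit 4; visit 8 is 4 to 14 days after visit 6; visit 9 is day 90 to 97. The recording window is 30 days after the last dose (section 10.2).

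**Participants who receive all three infusions**

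- Last dose (visit 6): 4 + 4 = day 8 to 21 + 21 = day 42.
- Last scheduled review (visit 8): 8 + 4 = day 12 to 42 + 14 = day 56.
- Window closes: 8 + 30 = day 38 to 42 + 30 = day 72.
- Days of the window after the last review: 30 − 14 = 16 to 30 − 4 = 26.
- As a share of the window: 16/30 = 53% to 26/30 = 87%.

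**Position of visit 9, by last infusion received**

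| Last infusion | Day of last dose | Window closes on day | Visit 9, days after last dose | Visit 9, days after window closes |
|---|---|---|---|---|
| Third (visit 6) | 8 to 42 | 38 to 72 | 48 to 89 | 18 to 59 |
| Second (visit 4) | 4 to 21 | 34 to 51 | 69 to 93 | 39 to 63 |
| First (visit 2) | 0 | 30 | 90 to 97 | 60 to 67 |

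The extremes come from pairing the earliest visit 9 with the latest dose and the reverse; for the third infusion, 90 − 42 = 48 and 97 − 8 = 89. In every case visit 9 falls after the window has closed, so no scheduled visit lies between visit 8 and the end of the window.

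**Early stoppers.** If the last treatment visit attended is an infusion visit (2 or 4), no scheduled review follows in the window and all 30 days are uncovered. If the participant still attends the session 1 to 5 days later (visit 3 or 5), 30 − 5 = 25 to 30 − 1 = 29 days remain uncovered.

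**Start of the window.** There is no comparable gap here: the visit 2 review can ask back over the 14 to 28 days since consent at screening.

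**Is the blank at visit 9 real?** The next row of Table 2, the concomitant medication review, is marked at visits 9 and 10, so the blank does not look like a fault in reading the table. The weekly calls in section 8.7 and the calls in the Table 2 footnote are described as appointment reminders, with no adverse event enquiry.

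**Other sources on expected events.** KSET and CADSS are scheduled at visits 2, 4, 6, 8, 9 and 10. The eCRF takes three sets of vital signs per infusion (section 8.9.1). BAI is scheduled at visits 2, 8, 9 and 10, and TLFB covers drinking. No listed instrument records device rash or venepuncture bruising.

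**The case against.** The strongest reply on the schedule is that section 10.2 sets a recording window and does not promise a visit throughout it. Reporting does not stop at visit 8: serious events are reportable to 30 days, serious adverse reactions until the last visit, and participants carry an out-of-hours contact card. Ketamine's short half-life, noted in section 3, puts the acute effects within the reviewed visits. This stands in part. The two places are mismatched rather than strictly contradictory, and the 53% to 87% counts days without enquiry. It is not a proportion of events missed. But these routes all need someone to raise the event, and they serve serious or urgent problems better than non-serious ones.

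On expected events, a reader might infer that they never enter the database and that harms therefore cannot be compared by arm. The protocol does not support that. Section 10.2.1 says entry is not required unless the event is serious; it does not forbid it. Section 10.1 makes dissociative, cognitive and balance effects serious if they persist two hours after the infusion, and persistent marked blood pressure rises are treated likewise. Unexpected events and all serious events are in the eCRF, and KSET, CADSS, vital signs, BAI and TLFB are planned for every participant in both arms. Nothing limits the DMC to adverse event forms. For most of the listed effects, scales given to everyone suit an arm comparison better than variable form entries. An extra eCRF tick list of expected events would largely duplicate them and is a matter of preference.

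What remains is that these measures replace adverse event records only partly. They are taken at set times and do not give onset or causality as adverse events. BAI does not attribute anxiety to the therapy sessions. As the table reads, CADSS at visit 2 is footnoted as pre-infusion only while KSET is pre- and post-infusion, though superscripts in the extracted table may be unreliable.

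**Conclusion.** The schedule gap holds. For participants who receive all three infusions, 16 to 26 of the 30 days after the last dose (53% to 87%) have no scheduled adverse event enquiry. For those who stop early and attend only visits 9 and 10, it can be the whole window. Non-serious events in that period may be under-counted. This is a risk of unknown size: the protocol gives no event rates, and spontaneous reports are not excluded. The figures assume visits within the Table 2 windows and no enquiry outside the marked visits.

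The point on expected events holds only narrowly: form-based counts of non-serious expected events by arm will be incomplete. It does not follow that the main drug effects go unmeasured or that a clean safety comparison would be an artefact of collection. Device rash and venepuncture bruising are the main events left without a structured measure, and nothing in the protocol suggests that these would differ by ketamine dose.

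**What to change.** Reconcile Table 2 with sections 10.2 and 8.12 by marking an adverse events review at visit 9. It should ask back to 30 days after the participant's last infusion and record onset dates, so that events can be placed inside or outside the window. For those who receive all three infusions the window ends on day 38 to 72. For those who stop after the first or second it ends on day 30 or day 34 to 51, so the question should be tied to each person's own last dose date.

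The cost is one mark in the table at an existing visit and slight extra data entry. The real downside is recall: visit 9 is 48 to 89 days after a third infusion, and up to 97 days after the last dose for someone who stopped after the first. Recall over that span is imperfect, but better than no enquiry.

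For expected events, state that comparison by arm of the section 10.2.1 effects rests on KSET, CADSS and the recorded vital signs, and label adverse event form counts of non-serious expected events as incomplete. Note that device rash and venepuncture bruising have no such substitute. This needs no new data collection and changes no dose or clinical rule.
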